7.2 Outcome measures

Primary outcome measure:

The primary outcome measure, improvement in NAFLD from the start of treatment to the end of treatment at 52 weeks, is defined for each patient as:

- Improvement in NAS score by 2 or more points, and
- No worsening of the fibrosis score

Secondary outcome measures:

- *Conversion from a diagnosis of NASH to not-NASH.* For the subset of patients with NASH at enrollment, determine the proportion whose 52-week liver biopsy results in a centrally determined histological diagnosis of not-NASH
- *Change in NAS*. Change in NAS, is defined for each patient, as the difference in 52 week vs. baseline NAS scores
- *Specific histologic features.* Changes in specific histological scores, defined for each patient, as the difference in 52 weeks vs. baseline, in the following histological features from centrally scores liver biopsies:
 - **o** Fibrosis
 - o Steatosis
 - Lobular inflammation
 - Portal chronic inflammation
 - **o** Ballooning

Change from stage 1b to 1a fibrosis. For the subset of patients with stage 1b fibrosis at baseline, determine the proportion whose 52-week liver biopsy results in a centrally determined histological diagnosis of fibrosis 1a.

• *Serum aminotransferase*. Change in serum aminotransferase, is defined for each patient, as the difference in 52 week vs. baseline serum aminotransferase

- *Gamma-glutamyl transpeptidase*. Change in serum gamma-glutamyl transpeptidase, is defined for each patient, as the difference in 52 week vs. baseline serum gamma-glutamyl transpeptidase
- *MRI-determined hepatic fat fraction*. Change in MRI-determined hepatic fat fraction is defined for each patient, as the difference in 52 week vs. baseline MRI-determined hepatic fat fraction
- *Markers of oxidation and anti-oxidant status*. Change in markers of oxidation and anti-oxidant status, is defined for each patient, as the difference in 52 week vs. baseline values of the following markers:
 - o Malondialdehyde,
 - o F2alpha-isoprostane,
 - o Total antioxidant capacity, and
 - Oxidized LDL
- *Fasting insulin.* Change in fasting insulin, is defined for each patient, as the difference in 52 week vs. baseline fasting insulin
- *Fasting glucose*. Change in fasting glucose, is defined for each patient, as the difference in 52 week vs. baseline fasting glucose
- *Obesity measures.* Change in obesity measures, is defined for each patient, as the difference in 52 week vs. baseline values of the following obesity measures:

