7.3 Statistical analysis

Primary outcome measure:

Statistical analyses for the primary hypothesis will follow the intention-to-treat paradigm, which means that all randomized patients with baseline and 52 week liver biopsies will be included in the treatment group to which they were assigned. Any randomized patient who does not have the requisite biopsies will be accounted for and compared by assigned treatment group.

Since the primary outcome measure, defined in Section 7.2, is a binary indicator of improvement in histologic activity score after 52 weeks of treatment compared to baseline and since the randomization is stratified by clinic, P-values will be derived from the Mantel-Haenszel $\chi 2$ test for stratified 2x2 tables. The proportion of patients improved in the group assigned to cysteamine DR will be compared to the group assigned to placebo and a two-tailed p-value of ≤ 0.05 will be considered statistically significant.

Secondary outcome measures:

Statistical analyses for the secondary measures that are continuous measures or scores will be carried out using separate bootstrapped mixed-effects-models corresponding to each individual change measure (defined in Section 7.2) as the response variable, with random effects for variation by clinic, and an indicator variable for comparing cysteamine DR (compared to placebo). The regression coefficient estimate for the indicator variable is the treatment effect for each secondary measure and is interpreted as the mean of the per-patient differences in each secondary outcome measure in the cysteamine DR group minus the corresponding mean differences in the placebo group. Statistical significance for each secondary treatment effect will be achieved if zero is not included in the nominal 95% bootstrapped confidence limits for each secondary measure. Bootstrapping with 2,000 replications will be performed to achieve 95% confidence limits that account for, in advance,

potential non-normality in the continuous secondary outcomes measures or scores. The bootstrapping estimation will be carried out using Stata software.

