7.5 Justification of sample size

A total of 160 participants in two groups of equal size (80 per group) will be included to compare the efficacy of cysteamine DR vs. placebo with the primary outcome measure of histological improvement in NAS (as defined in section 7.2). A sample size of 160 patients with 1:1 randomization would provide 90% power to the study hypothesis to detect a significant difference between the two groups with a two-sided type I error rate of 0.05. This sample size takes into account that 10% of participants will not have 52 week biopsies and will be considered not improved based upon intention to treat analysis. The sample size estimation is based upon the assumption that the minimum clinically important difference, defined as a 33% lower relative rate of no histological improvement in the cysteamine DR group vs. the placebo group, will be expected with the assumed response rates in the placebo group of 75% (based on TONIC data and 2 to 1 split for patients not taking vs. taking vitamin E at the start of the trial) vs. expected percent with no histological improvement in NAS in the cysteamine DR group to be 50%. These sample size estimations are conservative and would have a minimal likelihood of a type 2 error.

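### Section 7.3 omits the baseline value from the models for the continuous secondary outcomes: the analysis stays valid, but precision is lost wherever week-52 values do not track baseline with a slope near 1

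*Protocol*

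**What the plan says.** Section 7.2 defines every continuous secondary measure as a simple within-patient difference; for the NAS, for example, change is taken "as the difference in 52 week vs. baseline NAS scores". Section 7.3 then fits "separate bootstrapped mixed-effects-models corresponding to each individual change measure (defined in Section 7.2) as the response variable". The terms on the other side of the model are only these: "with random effects for variation by clinic, and an indicator variable for comparing cysteamine DR (compared to placebo". It states that the treatment coefficient "is interpreted as the mean of the per-patient differences in each secondary outcome measure in the cysteamine DR group minus the corresponding mean differences" for placebo. An outcome counts as significant "if zero is not included in the nominal 95% bootstrapped confidence limits for each secondary measure". The same section sets the number of bootstrap replications and names the software.

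No baseline term for the outcome appears in sections 7.2, 7.3 or 7.4. Section 3.2 stratifies randomization by clinical center and by baseline weight category; weight category is not in the model either.

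**The concern.** Every one of these outcomes has a baseline value by construction, since otherwise there would be no change score. A model for raw change fixes the slope of the week-52 value on the baseline value at 1. Where the true slope differs from 1, part of the baseline variation stays in the residual, and a chance difference between groups at baseline moves the treatment estimate.

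Counting ALT and AST separately, about 21 outcomes use this model: NAS, five histologic features, ALT, AST, GGT, MRI fat fraction, four oxidation markers, fasting insulin, fasting glucose, four body measures and PedsQL. Apart from the link to weight category, their baselines are balanced between groups only by chance. Significance is decided by whether the interval excludes zero, so interval width bears directly on what is reported. The protocol states no power or precision for any of them.

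**Working it through.** **The plan's own figure.** The only sample-size figure is for the binary primary outcome. Section 7.5 plans "A total of 160 participants in two groups of equal size (80 per group") and claims 90% power for it at a two-sided type I error of 0.05. With non-improvement of 75% against 50% and an uncorrected chi-square test, n = [1.960·√(2·0.625·0.375) + 1.282·√(0.75·0.25 + 0.50·0.50)]² / 0.25² = 76.7, so 77 per group. With 80 per group the power is 91.2%. This takes the 75% and 50% as already including missing biopsies. The stated figure is reproduced, but it does not bear on the continuous outcomes.

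**Inputs.** From section 7.3: response, model terms and interpretation. From section 7.5: 80 per group with 10% lacking a week-52 biopsy, so about 72 per group with a measured change. Not in the protocol: the baseline SD s0, the week-52 SD s1 and their correlation r. These are assumed over a range.

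**Step 1, residual variances.**
- Planned model: s0² + s1² - 2·r·s0·s1.
- Same model with the baseline covariate: s1²·(1 - r²).
- Difference: (s0 - r·s1)². This is never negative, and is zero only when the slope r·s1/s0 equals 1.

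**Step 2, equal SDs (in units of s²).** The width ratio is √(2/(1+r)).

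| r | planned, 2(1-r) | adjusted, 1-r² | variance ratio | width ratio |
|---|---|---|---|---|
| 0.3 | 1.40 | 0.91 | 1.54 | 1.240 |
| 0.5 | 1.00 | 0.75 | 1.33 | 1.155 |
| 0.7 | 0.60 | 0.51 | 1.18 | 1.085 |
| 0.9 | 0.20 | 0.19 | 1.05 | 1.026 |
| 0.95 | 0.10 | 0.0975 | 1.03 | 1.013 |

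Take an effect that has 80% power under baseline adjustment with 72 per group. The planned model has about 62%, 68% and 73% power at r = 0.3, 0.5 and 0.7.

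**Step 3, unequal SDs.**
- Baseline SD smaller, s0/s1 = 0.6. With s1 = 1 the variance ratio is (1.36 - 1.2r)/(1 - r²): 1.000/0.910, 0.760/0.750 and 0.520/0.510 at r = 0.3, 0.5 and 0.7. Planned intervals are 4.8%, 0.7% and 1.0% wider.
- Week-52 SD 1.2 times baseline: 14.6%, 7.2% and 1.7% wider at the same r.
- Week-52 SD 0.8 times baseline: 41%, 32% and 26% wider.

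**Step 4, where the loss comes from.** With equal SDs, 2(1-r) = (1-r²) + (1-r)². The excess (1-r)² is exactly the variance contributed by the term -(1-r)d. With 72 per group, d has a standard error of √(2/72) = 0.167 baseline SD. An imbalance of 1.96 standard errors (0.327 SD) moves the planned estimate by 0.23, 0.16 or 0.10 SD at r = 0.3, 0.5 or 0.7. The standard errors of the planned estimate at those values are 0.20, 0.17 and 0.13 SD.

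**Step 5, simulation.** 4,000 runs at each r, 144 patients, 16 per clinic, clinic effects fitted as fixed terms, equal SDs.
- Standard-error ratios were 1.239, 1.142, 1.079 and 1.012 at r = 0.3, 0.5, 0.7 and 0.95.
- The slope of the planned estimate on d was -0.72, -0.49, -0.30 and -0.06. With the baseline covariate it was between -0.03 and 0.01.
- Both estimates averaged about zero, the true effect.

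**Step 6, cost of the extra term.** At 144 patients, one more coefficient costs a variance factor of about 1 + 1/140 = 1.007. With equal SDs this outweighs the gain only for r above about 0.986.

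**The case against.** The strongest reply is that nothing here is invalid. Under randomization the difference in mean change is unbiased, its interval covers correctly and the type I error is not inflated. The plan states a coherent quantity and estimates it. All of this stands, and a reader who infers from the missing covariate that the planned results would be biased or the tests unsound goes further than the documents allow.

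Four other inferences also fail:
- **Every interval is widened to a useful degree.** Not where the slope is near 1, which is plausible for height or weight.
- **The NAS entry threshold of 4 or more builds in a bias.** It applies to both arms, so regression to the mean cancels in the contrast. If anything, truncating NAS at entry tends to shrink the baseline SD, which reduces the gain for that outcome.
- **Wider intervals and carried-over imbalance are two separate harms.** Step 4 shows that, with equal SDs, they are the same quantity.
- **The primary result is at risk.** Its Mantel-Haenszel test and its sample size do not use this model.

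It can also be said that an analysis plan not shown here might add covariates, and that section 7.3 does not call its list of terms exhaustive. This carries less weight. The section fixes response, terms, interpretation, significance rule, replications and software, and the coefficient it describes is the unadjusted one. A plan that added baseline would depart from that sentence.

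Finally, secondary outcomes are reported at nominal levels with Bonferroni-corrected results alongside, so the consequence is limited. That is fair, and it bears on how much the point matters, not on whether it is right.

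**Conclusion.** The point holds as one of efficiency. Section 7.3 prescribes an unadjusted change-score model for about 21 continuous secondary outcomes when a more precise model is available from data already collected. Under equal SDs the planned intervals are about 24%, 15.5%, 8.5%, 2.6% and 1.3% wider at r = 0.3, 0.5, 0.7, 0.9 and 0.95. If the baseline SD is 0.6 of the week-52 SD, the figures are about 5%, 1% and 1% at r = 0.3, 0.5 and 0.7; if the baseline SD is the larger one, the loss exceeds the equal-SD figures at those correlations.

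The direction follows from algebra, in large samples. The size rests wholly on assumed SDs and correlations and will differ from outcome to outcome. The change is worth making; leaving the plan as it is would not invalidate any result.

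**What to change.** In section 7.3, add the baseline value of the outcome as a fixed covariate in each bootstrapped mixed model: change = baseline value + treatment indicator + random clinic effect. Reword the interpretation sentence so that the coefficient is the baseline-adjusted difference between groups in mean change, because after adjustment it no longer equals one group's raw mean change minus the other's.

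On a separate ground, baseline weight category can be added as a fixed effect: section 3.2 makes it a randomization stratum, and the analysis should reflect the stratification. The precision figures above do not depend on this.

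The cost is a short edit to section 7.3, made before unmasking, and one extra coefficient per model for the baseline value. No new data are needed, since each change score already requires the baseline value and weight category is recorded for randomization.

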7.4 Missing data

The occurrence of missing data in this trial is expected to be low and equally distributed across the treatment groups. We estimate that careful selection of patients during the screening phase and the consent process should result in no more than 10% missing data from patients who drop out before completing the 52 week treatment period. In primary, intention-to-treat analyses, subjects with missing data will be considered unimproved on the primary outcome measure.

The proportions with missing data will be compared across treatment groups using χ^2 tests. If the amount of missing data exceeds 10%, then a variety of sensitivity analyses will be carried out to compare to the primary analysis using all available non-missing data: (1) compare pessimistic and optimistic imputations of the missing values, (2) correct for missing data using multiple imputation with 10 replicated samples, and (3) use mixed random effects logistic or linear regression models, depending on the type of outcome measure. Sensitivity analyses (2) and (3) assume that that missing data are missing at random (MAR). It is possible that the missing data are not MAR and, therefore, non-ignorable. There are a few statistical methods available when there are non-ignorable missing data and these would be employed; however; all such methods involve strong assumptions that cannot be verified from the available data.

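### Section 7.4 makes the missing-data sensitivity analyses conditional on more than 10% missing, the plan's own expected ceiling, so a trial that runs to plan may never test how missing biopsies affect the primary result

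*Protocol*

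**What the plan says.** Section 7.4 of the protocol expects missing data to be "expected to be low and equally distributed across the treatment groups", and predicts that careful selection "should result in no more than 10% missing data from patients who drop out before completing the 52 week treatment period". Section 7.5 uses the same figure: "This sample size takes into account that 10% of participants will not have 52 week biopsies and will be considered not improved".

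For the primary outcome, Section 7.4 says that "subjects with missing data will be considered unimproved on the primary outcome measure"; the Design Synopsis agrees. Two checks carry no threshold. In Section 7.4, "The proportions with missing data will be compared across treatment groups using" chi-square tests. In Section 7.3, patients lacking the required biopsies are to be accounted for and compared by assigned arm.

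The sensitivity analyses do carry a threshold: "If the amount of missing data exceeds 10%, then a variety of sensitivity analyses will be carried out". They are (1) pessimistic and optimistic imputation, (2) multiple imputation with 10 replicates, and (3) to "use mixed random effects logistic or linear regression models, depending on the type of outcome measure". The protocol states that (2) and (3) assume data missing at random (MAR). It adds that methods for non-ignorable missingness would be used, but gives neither a method nor a condition for using one.

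**The concern.** The threshold sits where the plan expects the trial to end up at worst. If the trial loses what its sample size allows for, exactly 10%, the condition is not met and none of the three analyses is required.

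An overall amount is also the wrong thing to watch. When missing is scored as not improved, the bias in the difference between arms depends on the difference in missingness between them. Heavier loss on placebo favours the active drug, and heavier loss on active hides benefit. Equal loss is only an expectation.

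A second weakness concerns analysis (3). Each child has one biopsy after baseline, at week 52, and the primary outcome is a single yes/no value. A mixed logistic model therefore has no repeated outcome to borrow from. A child without the biopsy drops out of it, and what remains is an available-case analysis.

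At stake is whether a reader can tell if a positive or negative primary result depends on how at most 16 missing biopsies were scored.

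**Working it through.** **Inputs.** From Section 7.5 and the Design Synopsis: 80 per arm, two-sided 0.05, uncorrected chi-square, 75% against 50% not improved (25% against 50% improved), 10% without a 52-week biopsy. The splits of missing biopsies by arm, the counts improved and the null response rates below are assumptions, because the protocol gives none. Stratification by clinic is ignored throughout.

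**The plan's own figure.** Normal-approximation power for 75% against 50% at 80 per arm is 91.2%, which agrees with the stated 90%.

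**Where the threshold falls.** 10% × 160 = 16. Read as overall, the condition first holds at 17 missing. Read per arm, 10% × 80 = 8, and it first holds at 9 in either arm.

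**Can a conclusion turn below the overall threshold?** Take 16 missing (5 active, 11 placebo) and 30 against 18 improved. For a 2×2 table with cells a, b (active improved, not improved) and c, d (placebo), X² = N(ad − bc)² / (product of the four margins).

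- Missingness by arm, 5/80 against 11/80: 160 × 480² / (80 × 80 × 16 × 144) = 2.50, p = 0.11. Not flagged.
- Primary analysis (missing = not improved), 30/80 against 18/80: 160 × 960² / (80 × 80 × 48 × 112) = 4.29, p = 0.038.
- Available cases, 30/75 against 18/69: 144 × 720² / (75 × 69 × 48 × 96) = 3.13, p = 0.077.
- One of the 11 missing placebo children counted as improved, 30/80 against 19/80: 160 × 880² / (80 × 80 × 49 × 111) = 3.56, p = 0.059.
- Least favourable to active (all 11 placebo improved, all 5 active not), 30/80 against 29/80: 160 × 80² / (80 × 80 × 59 × 101) = 0.027, p = 0.87.

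With the same counts improved and an even 8/8 split, which escapes the threshold on either reading, the available-case p is 0.034 and the least favourable p is 0.51.

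**Average effect on type I error.** Assume equal response p among biopsied children in both arms. The spurious difference is p × (placebo missing − active missing)/80; for 5/11 that is 0.25 × 6/80 = 1.9 points to 0.50 × 6/80 = 3.8 points. Rejection rates are by exact binomial enumeration with 16 missing:

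| Missing, active/placebo | Chi-square p for missingness | Type I error at p = 25% | at p = 50% |
|---|---|---|---|
| 8/8 | 1.00 | 4.8% | 3.7% |
| 6/10 | 0.29 | 5.2% | 4.8% |
| 5/11 | 0.11 | 5.7% | 6.2% |
| 4/12 | 0.035 | 6.4% | 8.1% |
| 2/14 | 0.002 | 8.5% | 14.1% |
| 0/16 | 0.00002 | 11.5% | 22.8% |

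**Average effect on power.** Take 50% against 25% improved among biopsied children, using the same enumeration. An 8/8 split gives improvement rates of 45.0% and 22.5% and power of about 87% (86.0% by normal approximation). An 11 active/5 placebo split gives 0.50 × 69/80 = 43.1% and 0.25 × 75/80 = 23.4%, with power of about 77%.

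**The case against.** A reader might infer that unequal drop-out would go unchecked. The protocol does not support that. The chi-square comparison of missing proportions and the accounting by arm apply whatever the amount missing, so imbalance itself is always looked at. That objection stands in full.

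A reader might also infer a seriously inflated false-positive rate. The table shows otherwise. The large figures belong to 2/14 and 0/16, which the unconditional check would flag strongly, and the 4/12 split is flagged too. For splits that escape the check, type I error is about 6% at most. The power loss from heavier drop-out on active makes the efficacy test conservative.

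The threshold need not be overall. The sentence before it concerns proportions by treatment group, and on a per-arm reading 11/80 (13.75%) would already set the analyses in motion. The text settles neither reading; overall is the more natural one, because the 10% expectation and allowance are both stated for all participants.

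Nor is analysis (3) empty. It is written for every type of outcome and can help with those measured repeatedly, such as ALT. For the biopsy it still contrasts with missing-as-failure, and its MAR assumption is declared.

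What survives is that comparing missing proportions does not show their effect on the treatment comparison, and a significant chi-square triggers no further analysis. The sentence on non-ignorable methods does not fill this gap. Details of an imputation model may properly sit in the SAP, but the threshold is a rule the protocol itself fixes.

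**Conclusion.** The point holds in this limited form. The sensitivity analyses depend on a threshold equal to the plan's expected ceiling and sample-size allowance, and the wording leaves open whether it is overall or per arm. On the overall reading, a trial with up to 16 missing biopsies would have its missingness compared between arms but not its effect on the primary result.

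The consequence is fragility of a single conclusion more than a distorted error rate. With 16 missing, p can move from 0.038 to 0.077 (available cases) or 0.87 (least favourable imputation) at a split the chi-square does not flag, while average type I error stays near 6%. Power can fall from about 87% to 77% when loss is heavier on active. These sizes rest on the assumed splits, counts and response rates, and on unstratified tests. The least favourable imputation is a bound, not a plausible estimate.

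A related inconsistency needs its own correction: Section 7.3 says "all randomized patients with baseline and 52 week liver biopsies will be included in the treatment group to which they were assigned", while Section 7.4 counts patients without the biopsy as unimproved. In the illustration that choice alone separates p = 0.077 from p = 0.038, so which analysis is primary must be settled before a sensitivity analysis can be judged against it.

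**What to change.** In Section 7.4, delete the 10% condition and report these whatever the amount missing:

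- Analysis (1), pessimistic and optimistic imputation by arm, preferably as a tipping-point grid over the number of missing children counted as improved in each arm.
- Analysis (2), multiple imputation by arm from data already collected, such as baseline NAS, weight band and ALT at weeks 4 to 36. The model's details can go in the SAP.
- Analysis (3), kept for outcomes measured repeatedly. For biopsy outcomes, label it an available-case analysis under MAR, since there is one post-baseline biopsy.

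If a threshold is kept for any purpose, state whether it is overall or per arm. Keep the unconditional comparison of missingness by arm.

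The cost is a little more analysis work. No patients, visits or measurements are added, and the sample size stays at 160.

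### Ten imputations in section 7.4 are too few for the sensitivity P-value to be stable when it lies near 0.05; the primary test is unaffected

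*Protocol*

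**What the plan says.** Protocol section 7.4 expects no more than 10% missing data. In the primary intention-to-treat analysis, "subjects with missing data will be considered unimproved on the primary outcome measure". The section then adds a condition: "If the amount of missing data exceeds 10%, then a variety of sensitivity analyses will be carried out", to be set beside the primary analysis. Three are listed: pessimistic and optimistic imputation; a plan to "correct for missing data using multiple imputation with 10 replicated samples"; and mixed-effects regression. The second and third are stated to assume data missing at random. Methods for non-ignorable missingness are also mentioned.

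The significance criterion is in section 7.3 and belongs to the stratified Mantel-Haenszel test of the primary outcome: "a two-tailed p-value of ≤ 0.05 will be considered statistically significant". For continuous secondary outcomes the same section says "Bootstrapping with 2,000 replications will be performed to achieve 95% confidence limits".

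The number of imputations is therefore set by the protocol itself. The imputation model and the seed are not stated; those may properly be left to a statistical analysis plan.

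**The concern.** Multiple imputation draws the missing outcomes at random, so the pooled estimate, its standard error and its P-value carry simulation noise that shrinks as the number of imputations grows. Ten are usually enough for an efficient estimate. They are not enough for a P-value that another analyst could reproduce from the same data and model with a different seed.

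The 10% condition does not cause this noise, and it applies to all three sensitivity analyses. It does mean that the imputation analysis runs only where the noise is larger, because the noise grows with the fraction missing.

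At stake is how a borderline primary result is read. If it is just significant and the imputation P falls just above 0.05, readers will conclude that the finding is sensitive to missing biopsies, when the cause may be only the seed.

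**Working it through.** **Inputs.** From the protocol: 80 children per arm, two-sided 0.05, 25% versus 50% improved (75% versus 50% not improved), 10 imputations, run only above 10% missing. Assumed, because the protocol does not give them: missing rates of 12-30%, equal in both arms; outcomes missing at random within arm; imputation by arm from a Beta posterior (Jeffreys prior) followed by a binomial draw; pooling by Rubin's rules.

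**1. The plan's own figure.** Section 7.5 says the sample size "would provide 90% power to the study hypothesis to detect a significant difference between the two groups". Power = Φ[(Δ√n − 1.96√(2p̄(1−p̄))) / √(p₁q₁ + p₂q₂)]. With Δ = 0.25, n = 80 and p̄ = 0.625 this is Φ[(2.236 − 1.342)/0.661] = Φ(1.35) = 0.91. The stated 90% reproduces if the two rates already count missing biopsies as not improved.

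**2. Monte Carlo error.** As a share of the standard error it is about √(FMI/m), where FMI is the fraction of missing information and m the number of imputations. With imputation by arm only, FMI is close to the fraction missing.

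| Missing | m = 10 | m = 100 |
|---|---|---|
| 15% | √(0.15/10) = 0.12 | √(0.15/100) = 0.04 |
| 20% | √(0.20/10) = 0.14 | √(0.20/100) = 0.04 |

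This covers the estimate alone. With ten draws the between-imputation variance is also noisy, which the simulations below include. For borderline data sets, the SD of the P-value across seeds rises from 0.014 at 10% missing to 0.028 at 30%, with m = 10.

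**3. A data set whose primary result is significant.** Take 15% missing (12 of 80 per arm) and 29/68 versus 17/68 improved.
- Primary handling gives 29/80 versus 17/80. Uncorrected χ² = 160 × (29×63 − 51×17)² / (80×80×46×114) = 4.39, P = 0.036. This is unstratified; the planned clinic-stratified P would differ slightly.
- The observed data are then held fixed, the imputation is repeated with many seeds, and the share of seeds with P > 0.05 is counted:

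| Pooled quantity | m = 10 | m = 100 |
|---|---|---|
| Log odds ratio, small-sample (Barnard-Rubin) df | about 14% | about 1 in 8,000 |
| Log odds ratio, large-sample df | about 11% | about 1 in 8,000 |
| Risk difference, small-sample df | about 8% | none |

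With m = 100 the P-value is about 0.03 under all three, in agreement with the primary result.

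**4. Data closer to the line.** With 28/68 versus 17/68, pooling log odds ratios, the 5th-95th percentile of P is 0.029-0.085 with m = 10 and 0.041-0.058 with m = 100. So 100 imputations narrow the range but do not remove seed dependence when the converged P sits almost exactly at 0.05. Pooling risk differences, the 95% range is 0.036-0.054 with m = 100 and 0.041-0.047 with m = 1,000.

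**5. Data at the design rates.** With 34/68 versus 17/68 and m = 10 (risk differences), the median P is 0.0025, the 95% range is 0.0008-0.0078, and no seed crosses 0.05.

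**6. How often two seeds disagree at 0.05,** among simulated trials with a significant primary result and 12-20% missing:

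| True improvement | m = 10 | m = 100 |
|---|---|---|
| 50% vs 25% (design) | 1.6-3.3% | 0.4-0.7% |
| 40% vs 25% | 5.6-8.3% | 1.3-2.8% |

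**The case against.** The strongest objection is that nothing is decided by this P-value. That stands. A reader might infer that the trial's conclusion depends on the seed, or that a re-run could turn a failed trial positive. The protocol does not support this: the primary analysis assigns missing outcomes deterministically, the 0.05 criterion belongs to that test, and the imputation is only compared with it, next to analyses that need no random draws.

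Nor does every borderline data set show a positive result being undermined. With 28/68 versus 17/68, the primary handling gives 28/80 versus 17/80 and P = 0.053, which is already not significant. With 26/64 versus 16/64 it gives 26/80 versus 16/80 and P = 0.072. The harm is confined to cases such as 29/68 versus 17/68, and at the design effect these are uncommon.

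Two further objections stand in part. The protocol schedules liver enzymes throughout follow-up and baseline histology is known, so an imputation model using them would carry less missing information; the figures above then lean high. The contrast with 2,000 bootstrap replications is also weak as evidence of inconsistency, because locating the tails of a distribution needs more draws than pooling a mean and variance. It shows only that computing time is not a constraint.

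A fixed seed would make the result repeatable, but one arbitrary draw from a wide distribution would still be reported. A larger number of imputations narrows that distribution.

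**Conclusion.** The point holds as a minor improvement to a sensitivity analysis. Ten imputations leave Monte Carlo noise of about 12-14% of a standard error at 15-20% missing. For a result near 0.05, that is enough to put the sensitivity P-value on the wrong side by chance: 8-14% of seeds in the worked example, depending on the scale and degrees of freedom used for pooling, against practically none with 100. The primary test and results far from 0.05 are unaffected.

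The sizes rest on assumed missing rates, data missing at random within arm, and imputation by arm without auxiliary covariates.

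**What to change.** In Protocol section 7.4, change the number of imputations in sensitivity analysis (2) from 10 to at least 100 imputed data sets, increased until the Monte Carlo error of the P-value is negligible, with a pre-specified random seed. The open-ended wording matters because 100 may still be too few when the converged P lies almost exactly at 0.05.

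This changes one phrase and adds negligible computing time. No patient, visit or procedure is affected, and the primary analysis stays as it is.
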